6 STUDY POPULATION

6.1 Study Entry Criteria

6.1.1 Inclusion Criteria

Patients must meet all of the applicable criteria to be eligible for enrollment in this study:

1. Willing and able to sign the approved informed consent.
2. Age: 18+ years old at Screening.
3. Diagnosis (a., b., and c. required) of **EITHER** *Acute Myeloid Leukaemia*:
 - a. By World Health Organization (WHO) criteria regardless of etiology, sub-type or treatment history.
 - b. High risk AML* diagnosis in accordance with one of the following classifications:
 - ≥ 60 years of age with AML who are **not** candidates for (based on parameters such as performance scores, co-morbidities and cytogenetic studies), or have refused, standard chemotherapy
 - 18+ year old with *de novo* or secondary AML (MDS/AML or treatment-related (t)-AML) who are **not** expected to benefit from standard remission-induction chemotherapy (unfavorable cytogenetics)
 - Relapsed/refractory AML after no more than 3 previous lines of chemotherapy, including hypomethylating agents, for whom no standard therapies are available
 - c. Eastern Cooperative Oncology Group (ECOG) performance status score ≤2.

*All forms of AML (M0–M7) diagnosed by morphologic, histochemical or cell surface marker criteria.

OR *Myelodysplastic Syndromes*:

- a. By WHO criteria regardless of sub-type.
 - b. High Risk MDS diagnosis in accordance with one of the following classifications:
 - MDS patients who have failed first-line therapy, demonstrated by resistance to, or relapse following a minimum of 4 cycles with a hypomethylating agent (HMA)
 - Treatment-related MDS, except if it is associated with favorable cytogenetics, and **not** a candidate for stem cell transplantation
 - c. Either an International Prognostic Scoring System (IPSS) score equivalent to intermediate-2 risk or higher, or a Revised International Prognostic Scoring System (IPSS-R) score equivalent to intermediate risk or higher.
4. Prior autologous stem cell transplant is allowed if a minimum of 3 months has elapsed from the time of transplant and the patient has recovered from transplant-associated toxicities.
 5. Prior allogeneic stem cell transplant is allowed, provided all of the following criteria are met:
 - a. Transplant was >120 days prior to study enrollment
 - b. No immunosuppressive medications have been taken for at least 1 month
 - c. No active graft versus host disease (GVHD), excluding Grade 1 skin GVHD

6. WBC $\leq 30 \times 10^9/L$ (30,000/ μL) for at least one week prior to first dose, with hydroxyurea use to achieve this value acceptable.
7. Platelet count $\geq 30 \times 10^9/L$ (30,000/ μL) prior to first dose, with transfusions to reach this limit acceptable.
8. Life expectancy >12 weeks.
9. Willing to discontinue all existing anti-neoplastic therapies (with the exception of hydroxyurea) for the 3 weeks prior to first dose of IMG-7289, total duration of dosing, and 1 week after last dose.
10. Amenable to serial bone marrow evaluation, blood, and urine sampling during the study.
11. Able to swallow capsules.
12. Agrees to use an approved method of contraception from Screening and until 28 days after the last administration of the study drug. Agreed methods of contraception may include: condom; use of birth control pills, patches, implants or injections, diaphragm with vaginal spermicide, intrauterine device (IUD) and/or surgical sterilization (vasectomy or tubal ligation at least six months prior to dosing). Patients practicing abstinence must agree to use an approved method of contraception should they become sexually active during the study.

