2 PROTOCOL SYNOPSIS

Protocol Title: A MULTI-CENTER, OPEN LABEL STUDY TO ASSESS THE SAFETY, PHARMACOKINETICS AND PHARMACODYNAMICS OF IMG-7289 WITH AND WITHOUT ATRA (TRETINOIN) IN PATIENTS WITH ADVANCED MYELOID MALIGNANCIES

Protocol No: IMG-7289-CTP-101

Investigator/Study Centers: Approximately 8 sites in Australia; additional sites and countries may be added as needed.

Study Hypothesis and Objectives:

Hypothesis: IMG-7289 with and without all-*trans* retinoic acid (ATRA; tretinoin) is a safe and tolerable orally available agent when administered to patients with advanced myeloid malignancies including high risk acute myeloid leukaemia (AML) and high risk myelodysplastic syndromes (MDS); lysine-specific demethylase 1 (LSD1) inhibition (LSDi) by IMG-7289 will have a negative impact on leukaemic and dysplastic cells, an effect which may be further enhanced *via* synergistic mechanisms when administered in combination with ATRA.

Objectives: The following objectives will be evaluated in patients with advanced myeloid malignancies, including high risk AML and high risk MDS, treated with IMG-7289 with and without ATRA:

Primary:

- Safety and tolerability
- Pharmacokinetics
- The adequacy of dose and duration in producing a pharmacodynamic effect

Secondary:

- The association of plasma concentrations (C_{max} and C_{min}) and exposure (AUC) on haematopoiesis (both short⁺ and longer-term[†] measures)
- The kinetics of recovery of haematopoiesis for a given dose and for a given duration of dosing

CCI

⁺Short term measures may include reticulocyte counts, absolute neutrophil counts (ANC), platelet volume.

[†]Longer-term measures may include return of counts to baseline or better.

CCI

Investigational Drug: The drug product is identified as IMG-7289, a bis-tosylate salt. The free base of IMG-7289 is an irreversible inhibitor of LSD1. The chemical name is: *N*-[[(2*S*)-5-[[[(1*R*,2*S*)-2-(4-fluorophenyl)cyclopropyl]amino-1-(4-methylpiperazin-1-yl)-1-oxopentan-2-yl]-4-(1*H*-1,2,3-triazol-1-yl)benzamide, bis-tosylate salt.

IMG-7289 will be supplied as capsules in multiple strengths. CCI

CCI

Additional Medication: Tretinoin (all-*trans* retinoic acid; ATRA; Vesanoid®) is an approved retinoid for the indication of induction of remission in acute promyelocytic leukaemia (APL; FAB classification AML-M3). Chemically, tretinoin is 3,7-dimethyl-9-(2,6,6-trimethylcyclohex-1-enyl) nona-2,4,6,8-all-*trans*-retinoic acid.

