There are two potential duration-extension pathways for the duration-finding cohorts: duration extension with IMG-7289 alone, or IMG-7289 administered in combination with ATRA. Therefore, prior to opening a duration-finding cohort, the DSMC will assess the safety and pharmacodynamic effects of the earlier sub-cohorts, and reach consensus on:

1. Whether it appears safe to extend the duration of IMG-7289 dosing
2. Whether there appears to be greater therapeutic benefit with IMG-7289 dosed in combination with ATRA.

Based on the above assessments, one of the below duration-finding cohorts will commence.

Cohort 3: Dosing of IMG-7289 at the D_p will begin on Day 1 for a duration of 14 days.

Cohort 3 χ : The above IMG-7289 regimen in combination with ATRA 45 mg/m² per day for 14 days.

Cohorts 3 and 3 χ will initially be allowed to receive **2 cycles** of IMG-7289, provided IMG-7289 (with or without ATRA) continues to be tolerated.

The duration of dosing will be extended in subsequent cohorts provided that:

1. A minimum of 3 patients from the previous cohort have completed Cycle 1, both the applicable dosing and rest periods
2. The number of patients who experience DLT is within the guidelines (Section 8.2.2)
3. DSMC review of the previous cohort has determined that:
 - a. The duration of dosing appears safe
 - b. Further duration extension is appropriate

If the DSMC determines further duration extension is appropriate, then additional cohorts will be dosed with extending durations to determine if a more optimal duration can be identified; possible cohorts are outlined below.

Cohort 4: Dosing of IMG-7289 will begin on Day 1 for a duration of 21 days.

Cohort 4 χ : The above IMG-7289 regimen in combination with ATRA 45 mg/m² per day for 21 days.

Cohorts 4 and 4 χ will initially be allowed to receive **1 cycle** of IMG-7289.

If the DSMC determines a specific dosing duration is associated with greater therapeutic benefit, patients who have fully completed their initially allowed IMG-7289 cycles and are at a different dosing duration will be transitioned to the more optimal dosing duration at the start of their next cycle.

The table below summarizes the duration-finding phase by cohort, dosing duration, treatment regimen, rest period and number of initially allowed IMG-7289 cycles.

Cohort	IMG-7289 Dose (free base)	IMG-7289 Cycle		No. of Initial IMG-7289 Cycles**
		Dosing Duration	Rest Period*	
3	$D_p^{\text{§}}$	14 days	7 days	2

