3.4 Background to All-*Trans* Retinoic Acid (ATRA; tretinoin) Use in Acute Leukaemia

The standard “7+ 3” treatment regimen can be expected to achieve a complete remission rate approximating 80%. AML is, however, infrequently cured with chemotherapy. The outstanding exception is acute promyelocytic leukaemia (APL) which, when treated with all-*trans* retinoic acid (ATRA) in combination with other agents such as As_2O_3 , can achieve a *cure* rate approaching 90% (Wang and Chen 2008; Lo-Coco *et al.*, 2013). The primary mechanism by which ATRA is thought to achieve its therapeutic effects is by converting the fusion oncoprotein PML-RAR α from a transcriptional repressor to a transcriptional activator and inducing its own proteolysis. Transcriptional activation drives myeloid differentiation, but that alone is not sufficient to clear leukaemic stem cells; ligand-induced degradation of this oncoprotein is more closely linked to clinical efficacy (de The' *et al.*, 2012; dos Santos *et al.*, 2013). Granulocytic differentiation can be induced at low ATRA doses, but higher doses are required to induce PML-RAR α proteolysis and reduce the frequency of leukaemic stem cells (Nasr *et al.*, 2008). Thus, with APL, differentiation alone is not sufficient for cure.

While ATRA as monotherapy induces haematologic remission in virtually all cases of APL, patients invariably relapse because of residual disease; a surviving population of leukaemic stem cells (Warrell *et al.*, 1991) present at remission. This remnant of disease may be partially owing to inadequate exposure to ATRA. Orally administered ATRA is rapidly metabolized with a plasma elimination half-life of 0.8 hours (Muindi *et al.*, 1992b). When administered over a period of as

little as a week, C_{max} and exposure (AUC) are reduced by as much as 50% and 90%, respectively (Muindi *et al.*, 1992a; Adamson *et al.*, 1995). That a liposomal formulation of the drug effected cures as monotherapy in treatment-naïve APL patients supports the notion that ATRA exposure must attain, and remain, above a certain threshold to achieve maximal clinical effects (Tsimberidou *et al.*, 2006).

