3.7 ATRA Dose and Duration in Non-APL AML

There are no clinical studies comparing doses of ATRA in the treatment of APL. The standard dose is 45 mg/m² per day in divided doses, though some reports suggest that a reduced dose of 25 mg/m² is equally effective (Tallman and Altman 2009). Daily dosing of ATRA is typically continued until complete remission (CR) by clinical measures has been achieved, as long as the patient is tolerating treatment well. Patients who have received ATRA for at least two weeks but were discontinued because of toxicity even eventually achieved CR. After the induction of CR, APL patients receive intermittent ATRA for up to 2 years to achieve a molecular remission.

Though very low doses of ATRA in combination with IMG-7289 were needed to induce differentiation in cultured AML cells, higher exposure to ATRA than that needed for differentiation may be required to induce AML cell death (apoptosis) and potentially reduce the leukaemic stem cell pool. Hence, in combination with IMG-7289, the proposed dose of ATRA is 45 mg/m² per day divided into two doses.

The objective of this phase of the study is to expose leukaemic cells to a combination of both IMG-7289 and ATRA. Non-clinical models had suggested the half-life of IMG-7289 was less than 24 hours. The PK parameters now available for the first four dose-finding sub-cohorts indicate a drug half-life of 4-5 days. Thus, what was originally defined as the 7 day “rest” period is one during which patients are still exposed to IMG-7289 at or above the IC₅₀ of the drug. This degree of exposure has, however, been demonstrated to be well tolerated. Thus, to match more closely the exposure of ATRA to IMG-7289, ATRA will be given at the planned dose of 45 mg/m², but for 21 days, followed by a rest period of 7 days. This dosing schedule of ATRA is regarded as safe as it affords less exposure than standard recommended treatment regimens of ATRA for acute promyelocytic leukaemia in which 45-60 days of daily ATRA at 45 mg/m² would be most common.

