6.1.2 Exclusion Criteria

Patients will be excluded from the study if they meet any of the following criteria:

1. Has received either: immunotherapy within <8 weeks; chemotherapy within <3 weeks (with the exception of hydroxyurea); radiation therapy to $>30\%$ of marrow-bearing bone within <2 weeks prior to starting study treatment; or, has not yet recovered from the effects of such therapies (excluding alopecia).
2. Has undergone major surgery ≤ 4 weeks prior to starting study drug or has not recovered from side effects of such surgery.
3. Has undergone any surgical procedure within 2 weeks, excluding minor procedures (i.e., skin biopsy or central venous catheter placement/removal) prior to starting study drug.
4. Scheduled haematopoietic stem-cell transplant.
5. Current use of a prohibited medication including anticoagulants or platelet inhibitors or expected to require any of these medications (outside of such use permitted as per the Prohibited Medications section) during treatment with the investigational drug.
6. Current use of monoamine oxidase A and B inhibitors (MAOIs).
7. Known immediate or delayed hypersensitivity reaction or idiosyncrasy to drugs chemically related to IMG-7289, LSD1 inhibitors, or ATRA that contraindicates participation.
8. Uncontrolled active infection.
9. Clinical evidence of central nervous system (CNS) or pulmonary leukostasis, disseminated intravascular coagulation, or CNS leukaemia.
10. A concurrent second active and non-stable malignancy (patients with a concurrent second active but stable malignancy, such as non-melanoma skin cancers, are eligible).

11. Known human immunodeficiency virus (HIV) infection or known active Hepatitis B or Hepatitis C virus infection.
12. History of any illness/impairment of gastrointestinal (GI) function that might interfere with drug absorption (e.g., chronic diarrhea), confound study results or pose an additional risk to the patient by their participation in the study; patients with gastric bypass surgery.
13. Refractory to platelet transfusion (but not excluding patients receiving HLA-matched platelets that increment appropriately).
14. Evidence at the time of Screening of risk of bleed, including any one of the following:
 - a. Activated partial thromboplastin time (aPTT) ≥ 1.3 x the local upper limit of normal
 - b. International normalized ratio (INR) ≥ 1.3 x the local upper limit of normal
 - c. History of severe thrombocytopenia unrelated to AML, MDS or treatment for either

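### Eligibility admits acute promyelocytic leukaemia (M3), although the ATRA rationale is for non-APL AML; an APL remission in a small combination cohort could be read as combination benefit

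*Protocol*

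**What the plan says.** **Eligibility.** Protocol Section 6.1.1, criterion 3a, accepts AML "By World Health Organization (WHO) criteria regardless of etiology, sub-type or treatment history". The footnote to criterion 3b adds "All forms of AML (M0–M7) diagnosed by morphologic, histochemical or cell surface marker criteria". The synopsis repeats both. Criterion 3b also requires one of three high-risk routes, the first of which is open to patients aged 60 or over who are not candidates for, "or have refused, standard chemotherapy".

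**M3 is APL in the protocol's own terms.** The synopsis describes tretinoin as an "approved retinoid for the indication of induction of remission in acute promyelocytic leukaemia (APL; FAB classification AML-M3"). Table 9 in Section 16.2 lists APL with PML-RARA among the AML entities.

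**Exclusions.** None of the 17 criteria in Section 6.1.2 names APL, M3, t(15;17) or PML-RARA. The nearest is criterion 9: "Clinical evidence of central nervous system (CNS) or pulmonary leukostasis, disseminated intravascular coagulation, or CNS leukaemia". Criterion 14 adds limits on aPTT and INR and lists known DIC.

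**ATRA rationale.** Section 3.7 is headed "ATRA Dose and Duration in Non-APL AML". Section 3.4 states: "While ATRA as monotherapy induces haematologic remission in virtually all cases of APL".

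**Use of the result.** Before opening a duration-finding cohort, the DSMC must reach consensus on this question: "Whether there appears to be greater therapeutic benefit with IMG-7289 dosed in combination with ATRA" (synopsis and Section 8.1). A finding of greater benefit also moves monotherapy patients who have completed their initial cycles to the combination (Section 7.2.2.1).

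**Analysis.** The SAP states that the study is not randomised (IV.D) and that there is no covariate adjustment (VI.F). Its Efficacy Population carries no sub-type condition (VI.J). The objective response rate (ORR) covers AML and MDS together and counts stable disease as response (VIII.A).

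**The concern.** The study asks whether IMG-7289 acts on leukaemic cells and whether ATRA adds to that effect. In APL, by the protocol's own account, ATRA produces remission unaided. A remission in an APL patient on the combination therefore says almost nothing about IMG-7289 or about synergy.

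The eligibility text nevertheless lets that patient in by explicit wording, so a site enrolling one would be following the protocol. Every cohort in Section 7.2.2 receives IMG-7289, so no ATRA-alone group exists against which to recognise the effect, and no SAP rule sets the patient aside. What is at stake is the DSMC's choice between extending duration with or without ATRA, and the transfer of monotherapy patients that may follow, when a cohort may hold only three patients.

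**Working it through.** **1. Can an APL patient qualify?** Taking the three routes in criterion 3b in turn:

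- Route 1 (aged 60 or over, not a candidate for or refusing standard chemotherapy): no sub-type condition, so it is open to APL.
- Route 2 (not expected to benefit from induction chemotherapy): tied to unfavourable cytogenetics.
- Route 3 (relapsed or refractory): requires that no standard therapy is available. An APL patient here would presumably have used up ATRA already.

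The DIC and coagulation exclusions remove some APL patients but not APL as such. The eligibility lists are printed in full in both places, so text blacked out elsewhere does not account for the gap. Entry is possible, mainly by route 1.

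**2. Inputs.** Cohort size n = 3 is the planned minimum (Protocol Section 12.2). The documents give no response rates, so these are assumed: non-APL response p = 5%, 10% or 20%; APL response on ATRA q = 50% or 95%. The plan states no response-based sample-size calculation, so there is no figure of its own to reproduce.

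**3. Observed rate.** One remitter in three contributes 1/3 = 33 percentage points. If nobody else responds, ORR moves from 0/3 (exact 95% CI 0–70.8%) to 1/3 (0.8–90.6%).

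**4. Chance of at least one responder, and expected ORR.**

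- No APL patient: P = 1 − (1 − p)³; expected ORR = p.
- One APL patient among three: P = 1 − (1 − q)(1 − p)²; expected ORR = (q + 2p)/3.

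With p = 10%:

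- No APL: 1 − 0.9³ = 27%; expected ORR 10%.
- q = 50%: 1 − 0.5 × 0.81 = 60%; expected ORR (0.5 + 0.2)/3 = 23%.
- q = 95%: 1 − 0.05 × 0.81 = 96%; expected ORR (0.95 + 0.2)/3 = 38%.

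| Assumed p | P(≥1), no APL | P(≥1), one APL, q = 50% to 95% | Expected ORR, no APL | Expected ORR, one APL, q = 50% to 95% |
|---|---|---|---|---|
| 5% | 14% | 55% to 96% | 5% | 20% to 35% |
| 10% | 27% | 60% to 96% | 10% | 23% to 38% |
| 20% | 49% | 68% to 97% | 20% | 30% to 45% |

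The expected shift in ORR is (q − p)/3. It shrinks as the base rate p rises, which is what counting stable disease as response would do.

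**5. Chance that an APL patient enters.** The documents give no share of APL among enrolled patients. For an assumed share f, the chance is 1 − (1 − f)ⁿ. Four combination cohorts (1χ, 1w, 3χ, 4χ) at the minimum of three give 12 patients.

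| Assumed f | Cohort of 3 | 12 combination patients |
|---|---|---|
| 1% | 3% | 11% |
| 5% | 14% | 46% |
| 10% | 27% | 72% |

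**The case against.** The case for leaving this alone has real content.

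- **Entry is narrow.** Only route 1 is clearly open, and the DIC and coagulation criteria narrow it further. This stands, and it is why the point is conditional.
- **Remission is not assured.** Section 3.7 describes ATRA for APL as typically given daily until remission, most commonly for 45–60 days, whereas sub-cohort 1χ gives 7 days on and 7 off. A patient with prior ATRA may not remit either, and Section 3.4 says that patients on ATRA alone relapse. This stands for 1χ and is why q runs down to 50%. It is weaker for the 14- and 21-day regimens, because Section 3.7 also reports eventual remission after at least two weeks of ATRA.
- **The DSMC does not act on a raw ORR.** The trial is open-label, the committee includes an AML specialist, and it weighs several markers together (Section 8.1). WHO diagnosis is recorded at screening (Section 16.1.1, note a), and AML type and genetic classification are summarised and listed (SAP VII.A). An APL case could well be recognised. This stands, but recognition is left to judgement: no rule says what to do with the case.

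A reader might infer three stronger things that the documents do not support. First, that an APL patient necessarily makes ATRA's effect pass for synergy; the patient must enter, remit and go unrecognised. Second, that an APL patient in a monotherapy cohort distorts the comparator; neither document gives the effect of IMG-7289 in APL. Third, that screening cytogenetics would catch the case; the visible text requires WHO diagnosis, reports cytogenetics where locally available (Section 10.1.1), and makes FISH subject to cost (Section 10.1.2).

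**Conclusion.** The mismatch is established from the text: the stated population includes M3, no exclusion removes it, and the ATRA argument is written for non-APL disease. It is a rule as written, not a missing detail.

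The consequence is conditional. If an APL patient enters a combination cohort and remits, that remission could be counted and read as combination benefit. In a cohort of three it adds up to 33 percentage points. At an assumed 10% non-APL response and 50–95% APL response, the chance of seeing at least one responder rises from 27% to 60–96%, and expected ORR from 10% to 23–38%.

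These sizes rest on assumed response rates, and stable disease counting as response would make the ORR shift smaller. At an assumed 1–5% APL share, a given cohort of three has a 3–14% chance of including such a patient. The point merits correction because a cohort of three can steer the study and the repair costs little.

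**What to change.** 1. **Protocol Section 6.1.1 and synopsis:** reconcile the M0–M7 footnote with the non-APL rationale by limiting the AML population to non-APL AML (not M3 / PML-RARA). Align the sub-type wording in criterion 3a.
2. **Protocol Section 6.1.2 and synopsis:** add a matching exclusion criterion for APL.
3. **SAP VI.J and VIII.A, and the pharmacodynamic summaries in X.A:** for any APL patient already enrolled or still eligible, pre-specify that the patient stays in the Safety Population, that combination response and PD summaries are made without that patient, and that the patient is reported separately.
4. **DSMC review (Protocol Section 8.1):** state that the comparison of combination with monotherapy is likewise made without APL patients.

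The cost is a short amendment, a few lines in the SAP and the loss of very few candidates. The amendment should also state how APL is ruled out at screening, since the visible text does not show that cytogenetic results will always be available by then.
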